It is known that chronic hyperglycaemia causes increased risk of diabetic complications. It is possible that both glucose variability and postprandial hyperglycaemia are independent risk factors for this as well. There is some evidence that glucose variability and postprandial hyperglycaemic are common occurrence for children who have T1D. However, there is a paucity of published data on the prevalence of postprandial hyperglycaemia after breakfast in children and young people with T1D and no evidence-base for how to manage this phenomenon. The need for long-term studies to examine glucose variability from CGM data and, for closer examination of postprandial glucose variability to elucidate methods to reduce this, has been highlighted (Tansey *et al.* 2016). Although this applies to all meals, focusing on minimising postprandial hyperglycaemia after breakfast is paramount. This can help ensure good control through the morning and rest of the day when children are at school and actively learning (Tansey *et al.* 2016).

Aim:

To describe the distribution and dispersion of glucose variability and postprandial hyperglycaemia following breakfast, in children and young people with type 1 diabetes (T1D), using measurements from Dexcom CGM.

Objectives:

- To determine the glucose variability diurnally and nocturnally and in the four-hour postprandial breakfast period using measurement of 'time in range', 'time above range' and 'time below range'.
- To determine the variability of glucose excursion, level and peak and the recovery time in the four-hour postprandial breakfast period.
- To determine the number and percentage of participants who achieved internationally agreed pre and postprandial glucose targets at breakfast time.
- To describe comparisons between all the above measurements and the variables of sex, age, disease duration, BMI, HbA1c, insulin dose/sensitivity and insulin regimen.
- To describe comparisons between all the above measurements and food compositions taken in the breakfast meal.
- To describe comparisons between the above measurements and carbohydrate and insulin adjustments, fluid intake and activities that took place during in the four-hour postprandial breakfast period.

Study design

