Primary and secondary outcome measures will be based on international guidelines and consensus DiMegloi *et al.* 2018; Battelino *et al.* 2019) of the metrics and target glucose levels to be used in CGM analysis in clinical practice. These are agreed to be:

Metrics:

- Mean glucose
- Glucose variability (GV) % coefficient of variation (COV) target ≤36%
- Time in range (TIR) % and time spent between 3.9-10mmol/I
- Time above target (TAR) % and time spent >10.1-<13.9mmol/l) and >13.9mmol/l
- Time below range (TBR) % and time spent 3.0-3.8mmol/l and <3mmol/l

Target glucose levels:

- TIR % of readings >70% or 16hr 48min
- TAR % of readings <25% or <6hr high and <5% 1hr 12min very high
- TBR- % of readings <4% or <1hr low and <1% or <15min very low

Primary outcome measure:

• Mean glucose (mmol/l) in the four-hour postprandial breakfast period calculated from the CGM measurements at 5 minutes intervals.

Secondary outcome measures – post prandial period:

• Number and percentage who had pre-prandial glucose in target Mean peak glucose level (mmol/l), mean time to peak (mins), mean time to recover (to pre-prandial levels) (mins) in the four-hour postprandial breakfast period

- TIR, TBR and TAR (% and time) in the four-hour postprandial breakfast period
- Comparisons of the above measurements between cohorts and breakfast meal compositions and drinks, snacks taken in the morning and activities and insulin adjustments taken in the 4-hour postprandial period.

Secondary outcome measures – glucose variability:

• TIR, TBR and TAR (% and time) between the hours of 06.00-22.00, 22.00-06.00 and 24-hour period.

Data analysis

This will be a mix of univariate, bivariate and multivariate analysis as this is best suited to describing, summarising and visualising these data. Outputs will include the distribution of glucose levels and diurnal, nocturnal and post-breakfast variability to determine the spread and dispersion of the data. As well as providing new evidence on this phenomenon, it will also assist in determining required sample size for any subsequent investigation including an intervention testing of effects on interstitial glucose levels arising from different food intakes.

Safety considerations

Recruitment/consent

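### The plan lists %CV (target at most 36%) as its glucose-variability metric, but no outcome uses %CV or SD; variability is measured only by TIR, TBR and TAR

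*Combined protocol and SAP*

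**What the plan says.** The Aim has two parts: "To describe the distribution and dispersion of glucose variability and postprandial hyperglycaemia following breakfast". Objective 1 covers the variability part and chooses TIR, TAR and TBR as its measures: "To determine the glucose variability diurnally and nocturnally and in the four-hour postprandial breakfast period using measurement of 'time in range", after which it names the other two range metrics.

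Outcome measures opens by saying "Primary and secondary outcome measures will be based on international guidelines and consensus" and then lists the agreed metrics. One entry is "Glucose variability (GV) % coefficient of variation (COV) target ≤36" (a percentage). Mean glucose, TIR, TAR and TBR are separate entries in that list.

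The outcomes follow:

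- Primary: "Mean glucose (mmol/l) in the four-hour postprandial breakfast period calculated from the CGM measurements at 5 minutes intervals".
- Secondary, post-breakfast: pre-prandial glucose in target, peak, time to peak, time to recover, and TIR, TBR and TAR over the four hours, with comparisons of these.
- Secondary, headed glucose variability: "TIR, TBR and TAR (% and time) between the hours of 06.00-22.00, 22.00-06.00 and 24-hour period".

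No outcome mentions %CV or SD. Data analysis promises outputs on variability by day, by night and after breakfast, but names no statistic for them.

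**The concern.** One section uses the same term in two ways. In the metrics list, glucose variability is %CV with a numerical target, and the range metrics are listed separately. In the outcome list, and in Objective 1, glucose variability is the range metrics. The one metric that carries the variability label and a target is assigned to no outcome and no time window.

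Time in range depends on both where a child's glucose sits and how widely it swings. A steadily high child and a widely swinging child can share the same TIR, and two children with the same relative swing can have very different TIR. If the outcome list is followed as written, the paper could report ranges under the name of variability without saying how many participants meet the CV target. The study is also meant to inform the design and sample size of a later intervention study, so the measure reported as variability will be carried forward.

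**Working it through.** **Inputs.** From the metrics list: TIR band 3.9-10 mmol/l; upper cut 13.9; lower cut 3.0; CV target 36%; TIR target above 70%; TBR targets below 4% (low) and below 1% (very low). The documents give no glucose mean or SD, so every distribution, mean and profile below is an assumption.

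**The plan's own figures.** The time equivalents of the range targets reproduce: 0.70 × 24 h = 16.8 h (16 h 48 min); 0.25 × 24 h = 6 h; 0.05 × 1440 = 72 min; 0.04 × 1440 = 57.6 min (stated as under 1 h); 0.01 × 1440 = 14.4 min (stated as under 15 min). The targets are thus expressed over 24 hours. The 36% is a cited threshold with no derivation to check.

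**Model.** For log-normal glucose with mean m and coefficient of variation c: s = √ln(1 + c²), μ = ln m − s²/2, F(x) = Φ((ln x − μ)/s). Then TBR = F(3.9), TIR = F(10) − F(3.9), TAR = 1 − F(10).

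**Check 1: CV fixed at 36%, mean varied.** s = √ln(1.1296) = 0.349. At m = 8, μ = 2.0185, so F(10) = Φ(0.814) = 0.792, F(3.9) = Φ(−1.883) = 0.030 and TIR = 0.762.

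| Mean (mmol/l) | TIR % | TAR % | TBR % |
|---|---|---|---|
| 8 | 76.2 | 20.8 | 3.0 |
| 10 | 56.3 | 43.1 | 0.6 |
| 12 | 36.3 | 63.6 | 0.1 |

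TIR moves by 40 percentage points and crosses the 70% target with no change in relative variability. Under a normal model the fall is from 68% to 29%.

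**Check 2: TIR fixed at 60%, CV varied.** For each c, solve F(10) − F(3.9) = 0.60 for the mean, taking the higher-mean solution.

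| CV % | Mean (mmol/l) | TAR % | Above 13.9 % | TBR % | Below 3.0 % |
|---|---|---|---|---|---|
| 25 | 9.68 | 40.0 | 5.6 | 0.02 | 0.0 |
| 36 | 9.66 | 39.2 | 11.2 | 0.8 | 0.07 |
| 50 | 9.25 | 34.4 | 13.6 | 5.6 | 1.6 |

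TIR, total TAR and the mean say little about which side of 36% a child is on. TBR and the extreme bands do move.

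**Check 3: every band fixed.** Two constructed profiles each have 3% of readings at 3.0-3.8, 67% at 3.9-10, 20% at 10.1-13.9 and 10% above 13.9, with one glucose value per band.

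- Values 3.7, 8.5, 10.8, 14.2: mean = 0.03 × 3.7 + 0.67 × 8.5 + 0.20 × 10.8 + 0.10 × 14.2 = 9.39; SD 2.05; CV 2.05/9.39 = 22%.
- Values 3.1, 6.5, 13.0, 19.0: mean = 0.03 × 3.1 + 0.67 × 6.5 + 0.20 × 13.0 + 0.10 × 19.0 = 8.95; SD 4.29; CV 4.29/8.95 = 48%.

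The two profiles are identical on every range outcome and lie on opposite sides of 36%. They are deliberately artificial. They show that the full set of range metrics does not determine CV, not that such pairs are common.

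**The case against.** The strongest reply is that the range metrics are used as a set, and the set responds to spread. That stands. In Check 2, going from CV 25% to 50% takes TBR from 0.02% to 5.6%, past the plan's 4% target; time below 3.0 from 0% to 1.6%, past its 1% target; and time above 13.9 from 5.6% to 13.6%. In the normal model, going from CV 20% to 50% at the same TIR takes TBR from 0.2% to 17.9%. A reader might infer that the planned outcomes cannot show variability at all, or that children on either side of 36% would look alike on them. Neither inference is supported.

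A reader might also infer that the study's main aim goes unmeasured. The Aim's second part, postprandial hyperglycaemia, is covered by the four-hour mean, peak, time to peak, recovery time and post-breakfast TAR. Objective 2 adds "To determine the variability of glucose excursion, level and peak and the recovery time in the four-hour postprandial breakfast period", though only for that window.

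Third, the outcomes are said to be based on a list that contains %CV, and Data analysis promises outputs on spread and dispersion. A reader could fairly expect %CV among them, so the documents do not say that %CV will never be reported. But neither sentence assigns it to an outcome or a window, and the outcomes are then enumerated without it.

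Last, Objective 1 chooses range metrics on purpose, in a descriptive study with no hypothesis test. That is a legitimate choice of outcome. It still conflicts with the label in the metrics list and needs reconciling.

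**Conclusion.** The point holds as an internal mismatch with a practical consequence. The plan's stated variability metric has a target but no outcome. The outcomes that carry the variability name mix spread with level, so they cannot show who meets the CV target, and the variability part of the aim is answered only indirectly.

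The text comparison needs no assumption. The sizes rest on assumed glucose distributions: at CV 36%, TIR runs from 76% to 36% (log-normal) or from 68% to 29% (normal) over means of 8 to 12 mmol/l; at TIR 60%, CVs from 25% to 50% are all possible. Real CGM distributions will give other figures, but mean level and spread will still both feed into TIR.

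No sample size, power or error rate is affected, and no data are lost, because %CV can be computed from the same readings. It is worth correcting before analysis, but it does not threaten the study.

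**What to change.** - Name within-participant %CV (100 × SD/mean of that participant's CGM readings in the window), with SD, as a glucose-variability outcome for the 24-hour, 06.00-22.00 and 22.00-06.00 windows.
- Report the number and percentage of participants at or below 36% for the 24-hour figure.
- Keep TIR, TAR and TBR as outcomes in all their planned windows, under their own name.
- Reword Objective 1 to match, so that variability is determined by %CV and SD, with the range metrics alongside.
- %CV or SD in the four-hour post-breakfast window (240/5 = 48 readings per breakfast) is optional and descriptive. The 36% target should not be applied there.

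The cost is a change of wording and a few more descriptive outputs from the 5-minute CGM data already collected. Participants do nothing more, and the recruitment target does not change.
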